- The subject's home allows rapid access to emergency treatment if required (ie, the subject must not live so remotely that a reasonable arrival time of an ambulance could not be predicted).
  - The investigator is contactable to support the health care provider (HCP) if needed.
  - UCB has not requested to limit the possibility to perform home visits (eg, based on DMC recommendation).

The investigator will be asked to complete a checklist confirming all criteria have been fully evaluated. This checklist will be shared with the UCB study physician and reviewed before IMP administration in a home setting can take place.

If at any time during the Treatment Period, the subject relapses according to the predefined criteria for relapse as specified in Section 4.1.2 using the subject's score on iRODS, INCAT, or maximum grip strength (assessed by site personnel), and supported by the medical judgement of the investigator, then rescue medication must be considered and the subject must be withdrawn from IMP (see Section 6.4 and Section 7.7.3). The subject will return to the SOC (ie, Ig treatment) as rescue medication at the time of relapse and will be stabilized over a period of 2 weeks to maximum 12 weeks starting from PEOT (Visit 17). At the end of the stabilization, the subject will continue SOC. The time required for follow-up since last IMP dose is 12 weeks. The stabilization visit schedule still applies (every 1 to 3 weeks) if the subject has not reached 12 weeks after the last IMP dose at the end of stabilization. The subjects in the placebo arm will be offered the possibility to enter in the OLE and be treated with rozanolixizumab once all subjects have completed the CIDP01 study, the study is unblinded, and key results are available.

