## 9 ASSESSMENT OF EFFICACY

### 9.1 iRODS

The iRODS questionnaire should be completed by the subject prior to dosing and before any discussion of their current health status with the treating physician or any other study assessments. Subjects will complete the iRODS questionnaire at the time points detailed in the schedule of study assessments (Table 5-1). The questionnaire will be given to the subject to complete and will then be recollected and checked, for completeness only, by study personnel other than the treating physician. Subjects should complete the questionnaires themselves, unaided, in a quiet location.

The iRODS is a linearly weighted patient-reported outcome measure (questionnaire) that specifically captures activity and social participation limitations in patients with CIDP. The iRODS scale was constructed based on the World Health Organization (WHO) International Classification of Functioning, Disability and Health, literature search, and patient interviews (van Nes et al, 2011). All 24 items of iRODS meet Rasch model expectations. The questionnaire consists of 24 items (including eating, taking a shower, walking a flight of stairs, standing for hours, etc.) and assesses a patient's perception of their ability to perform daily and social activities. Patients have 3 response options: 0=impossible to perform; 1=performed with difficulty; and 2=easily performed, performed without difficulty (van Nes et al, 2011). The raw sum scores of iRODS (range 0 to 48) will be translated to log odds units (logits), placing patients' estimates on the same logit scale. For easier interpretation the person locations can be translated to values changing from 0 (most severe activity and social participation restrictions) to 100 (no activity and social participation limitations).

Subjects will be asked to complete the iRODS questionnaire at every study visit except for nondosing Visits 3, 5, and 7.

In addition to the primary efficacy variable in which subjects will be assessed for the change from Baseline to Week 13 (Day 85) in their iRODS score, subjects will also be assessed for change from Baseline in iRODS scores at each scheduled assessment during the Treatment and Observation Periods. Other efficacy variables will also include subject experienced CIDP relapse (iRODS), defined as a clinically important deterioration, ie, an MCID-SE  $\leq -1.96$ , and time to CIDP relapse (iRODS) during the Treatment Period.

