#### **2.2.1.2 Other efficacy variable**

Preliminary definitions linked to assessment of relapse:

- **CIDP relapse (iRODS)** is defined as a clinically important deterioration from Baseline in iRODS score, ie, a MCID-SE of  $\leq -1.96$
- **CIDP relapse (adjusted Inflammatory Neuropathy Cause and Treatment, INCAT)** is defined as an increase from Baseline of at least 1 point in the adjusted INCAT score. The adjusted score is identical to the INCAT disability score except for the exclusion of changes in upper limb function from 0 (normal) to 1 (minor symptoms) or from 1 to 0
- **CIDP relapse (maximum grip strength as assessed by site personnel)** is defined as a clinically important deterioration from Baseline in grip strength as measured by site personnel, ie, a decline of  $>14\text{kPa}$

Other efficacy variables will include:

- Subject experienced **CIDP relapse (iRODS)** up to Week 13 (Day 85) after first treatment
- Time to **CIDP relapse (iRODS)** during the Treatment Period
- Values and change from Baseline in iRODS scores at each scheduled assessment during the Treatment and Observation Periods
- Subject experienced **CIDP relapse (adjusted INCAT)** up to Week 13 (Day 85) after first treatment
- Time to **CIDP relapse (adjusted INCAT)** during the Treatment Period
- Values and change from Baseline in adjusted INCAT score at each scheduled assessment during the Treatment and Observation Periods

- Subject experienced **CIDP relapse (maximum grip strength as assessed by site personnel)** up to Week 13 (Day 85) after first treatment
- Time to **CIDP relapse (maximum grip strength as assessed by site personnel)** during the Treatment Period
- Values and change from Baseline in maximum grip strength score (maximum of 3 assessments) taken by site personnel at each scheduled assessment during the Treatment and Observation Periods
- Values and change from Baseline in daily maximum grip strength score (maximum of 3 assessments) taken by the subject at the same time each day during the Treatment and Observation Periods
- Values and change from Baseline in Rasch-built, modified interval Medical Research Council scale (RT-MRC) sum score at each scheduled assessment during the Treatment and Observation Periods
- Values and change from Baseline in fatigue at each scheduled assessment during the Treatment and Observation Periods

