## 8.2 Statistical analysis of the other efficacy variables

### 8.2.1 CIDP relapse, MMRM and summary tables will be performed on the FAS and repeated for the PPS for iRODS, adjusted INCAT and clinician reported grip strength.CIDP relapse (iRODS)

CIDP relapse (iRODS) is defined as a clinically important deterioration from Baseline in iRODS score, i.e. a standardized change from baseline smaller than or equal to the minimum clinically important differences-standard error (MCID-SE) of  $\leq -1.96$ .

This standardized change from baseline refers to individual person-level responsiveness calculated by individual change divided by their corresponding SE of difference at a given timepoint. [Va15]

$$\text{"MCID - SE"} = \frac{\text{Standardized value}_{\text{Visit}} - \text{Standardized value}_{\text{Baseline}}}{\sqrt{\text{SE}_{\text{Visit}}^2 + \text{SE}_{\text{Baseline}}^2}}$$

Values and changes from Baseline in iRODS scores will be summarized by treatment group and for all participants and listed by treatment group at each scheduled assessment during the Treatment and Observation Period.

The point estimate and the corresponding 2-sided 90% CI for the difference between placebo and rozimab CIDP relapse rates up to week 13 will be reported. The CI will be constructed using the asymptotic standard error (asymptotic Wald confidence limits).

Analyses will be performed for the FAS utilizing the observed cases.

Sensitivity analysis for relapse will be performed in the same way, however for the PPS.

The rule for handling missing data is described in Section 4.2.1.

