#### **8.2.5 CIDP relapse**

The event of CIDP relapse is defined by occurrence of either relapse across the 3 calculated criteria: iRODS relapse, adjusted INCAT relapse and maximum grip strength as assessed by site personnel (14 kPa) relapse as defined in sections 8.2.1, 8.2.2 and 8.2.3 and 'other' as captured in the CRF by the investigator. It will be described and analysed in the same way as the individual relapse definitions. This will be done for the FAS and the PPS.

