## 13 APPENDICES

### 13.1 Conversion of iRODS scores

Table 13-1: Nomogram

R-ODS summed raw score	Rasch person location	centile metric	Corresponding SE
	(logits)		$SE = 0.4248 - 0.0016 * \text{location} + 0.0140 * \text{location}^2$
0	-6.95	0	1.11
1	-6.03	6	0.94
2	-5.36	11	0.84
3	-4.87	14	0.76
4	-4.48	16	0.71
5	-4.14	19	0.67
6	-3.84	21	0.64
7	-3.57	22	0.61
8	-3.32	24	0.58
9	-3.09	26	0.56
10	-2.87	27	0.54
11	-2.66	28	0.53
12	-2.46	30	0.51
13	-2.26	31	0.5
14	-2.07	32	0.49
15	-1.88	34	0.48
16	-1.70	35	0.47
17	1.52	36	0.46
18	1.33	37	0.45
19	-1.15	39	0.45
20	0.97	40	0.44
21	-0.79	41	0.43
22	-0.61	42	0.43
23	-0.42	43	0.43
24	-0.24	45	0.43
25	-0.05	46	0.42
26	0.14	47	0.42
27	0.34	48	0.43
28	0.53	50	0.43
29	0.73	51	0.43
30	0.94	52	0.44
31	1.15	54	0.44
32	1.36	55	0.45
33	1.58	57	0.46

R-ODS summed raw score	Rasch person location	centile metric	Corresponding SE
	(logits)		$SE = 0.4248 - 0.0016 * \text{location} + 0.0140 * \text{location}^2$
34	1.81	58	0.47
35	2.04	60	0.48
36	2.28	61	0.49
37	2.54	63	0.51
38	2.80	65	0.53
39	3.09	67	0.55
40	3.40	69	0.58
41	3.74	71	0.61
42	4.11	73	0.65
43	4.54	76	0.71
44	5.03	80	0.77
45	5.59	83	0.85
46	6.25	88	0.96
47	7.07	93	1.11
48	8.11	100	1.33

This document cannot be used to support any marketing authorization application and any extensions or variations thereof.  
PUBLIC COPY

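### The iRODS relapse cut-off of -1.96 is a one-visit rule applied at 12 visits without confirmation; the SAP should add a confirmed-relapse sensitivity analysis

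*SAP*

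**What the plan says.** SAP 8.2.1 standardizes each participant's change as "individual person-level responsiveness calculated by individual change divided by their corresponding SE of difference at a given timepoint". The denominator is the square root of the summed squares of the visit SE and the Baseline SE. Relapse is a standardized change at or below the "minimum clinically important differences-standard error (MCID-SE) of" -1.96.

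SAP 2.2.1.2 makes the variable relapse "up to Week 13 (Day 85) after first treatment", and SAP 8.2.1.1 adds time to relapse from Day 1 with a Kaplan-Meier display. On frequency, protocol 9.1 states: "Subjects will be asked to complete the iRODS questionnaire at every study visit except for nondosing Visits 3, 5, and 7". For the analysis, SAP 8.2.1 states that the point estimate and 90% Wald interval for the "difference between placebo and rozimab CIDP relapse rates up to week 13 will be reported". SAP 4.2.1 also counts withdrawal, missing Week 13 data and Ig rescue as relapse. SAP 8 labels all efficacy analyses exploratory, without p-values.

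No confirmatory assessment is required. Protocol 7.7.3 and 8.2 act on a crossing only when it meets the criteria "and supported by the medical judgement of the investigator"; the calculated variable in SAP 8.2.1 has no such filter.

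Protocol 14.3.2 leaves relapse sensitivity analyses to the SAP. For iRODS, SAP 8.2.1 supplies only a repeat of the same definition in the PPS.

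**The concern.** For a normally distributed standardized difference, -1.96 is crossed by chance 2.5% of the time in one comparison. The variable, however, is in effect the lowest of 12 such differences, and all 12 share one Baseline measured with error. One low score at one visit makes a participant relapsed for good, even if the next score is back at Baseline and the investigator saw no relapse.

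These crossings arise in both arms among participants who have not deteriorated. They raise both relapse rates, pull the difference towards zero and bring event times forward. An effective drug would look less effective on this variable, and no planned analysis would show how much of the result is single-visit noise.

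**Working it through.** **Inputs from the documents.** The criterion is in SAP 8.2.1. Locations and SEs are in SAP Table 13-1, whose SE formula begins "SE = 0.4248 - 0.0016" x location and ends + 0.0140 x location squared. The assessments are Visits 4 and 6 (2) and Visits 8 to 17 (10), so 12. SAP 2.4 gives 15 per arm. The documents state no false-relapse rate, so there is none to reproduce. The Table 13-1 SE column does reproduce from its formula, with a largest difference of 0.005. Raw scores 17, 18 and 20 are read as negative locations, which fits their order and their SEs; the missing signs may come from PDF extraction.

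**Size of a crossing.** Take Baseline raw 30 (location 0.94, SE 0.436).
- Raw 24 (location -0.24, SE 0.426): -1.18 / sqrt(0.436^2 + 0.426^2) = -1.18 / 0.609 = -1.94, no relapse.
- Raw 23 (location -0.42, SE 0.428): -1.36 / 0.611 = -2.23, relapse.

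**Stable participant, normal model.** Write the standardized change as z_k = (e_k - e_0) / sqrt(2), with e_0 the Baseline error. Given e_0 = u, a crossing at one visit has probability Phi(u - 1.96 sqrt(2)). With errors independent between visits,

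P(any of 12) = integral of phi(u) [1 - (1 - Phi(u - 1.96 sqrt(2)))^12] du = 16.0%.

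For one visit the formula returns 2.5%. Ignoring the shared Baseline would give 1 - 0.975^12 = 26.2%, which is too high.

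**Stable participant, Table 13-1.** Simulating the observed location around a fixed true value, rounding to the nearest table row and applying the SAP criterion gives, with independent errors, about 2-3% at one visit and 11-20% at any of 12 for true logits -2 to 6. An exact calculation on the raw-score distribution implied by the table gives 12-21% for true locations -1.0 to 4.5. Outside that range it gives 5-10%.

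**Dependence on the error structure (assumed, not in the documents).**

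| Assumption | Any of 12 visits |
|---|---|
| Independent, normal model | 16.0% |
| Week-to-week autocorrelation 0.2 / 0.5 / 0.7 / 0.9 | 15.0 / 12.4 / 8.8 / 2.0% |
| Time-constant share of error variance 10 / 20 / 30 / 50% | 13.0 / 10.2 / 7.3 / 2.5% |
| Correlation 0.2 / 0.4, Table 13-1 | 7-13% / 3-6% |
| Real weekly fluctuation adding 25% of the error variance | 22.9% |

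Correlation lowers the single-visit rate too. At correlations of 0.2 and 0.4 the any-visit rate is still six or more times the single-visit rate. At autocorrelation 0.9 it is about twice.

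**Dilution.** If true relapse rates are p_c and p_t and a share f of the others is falsely called, each observed rate is p + (1 - p) f. The difference is then (p_c - p_t)(1 - f). With assumed rates of 50% and 15% and f = 16%:
- 0.50 + 0.50 x 0.16 = 58.0%
- 0.15 + 0.85 x 0.16 = 28.6%
- difference 29.4 points instead of 35

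With 15 per arm, the chance that the 90% Wald interval lies above 0 falls from 70% to 50%.

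**Confirmed definition.** With independent errors, two consecutive crossings give a false rate of 2.8% (normal model). Also counting a first crossing at Week 13 gives 4.4%, or about 3-6% on Table 13-1. At 4.5%, under the same assumed rates, the difference is 33.4 points and the chance about 63%.

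**The case against.** A reader might infer that 12-20% of stable participants will be called relapsed. The documents do not support that as a fact. It needs independent errors across weekly self-completed questionnaires. The SAP denominator sets only the Baseline-visit covariance to zero and is silent on correlation among the 12 visits. The rate must stay conditional.

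A reader might also infer that -1.96 was chosen to hold false relapses at 2.5% and that the SAP breaches its own target. No such target or null hypothesis is stated. The protocol presents the value as a clinically important deterioration taken from published work.

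A third inference is that the composite in SAP 8.2.5 is worse still: "The event of CIDP relapse is defined by occurrence of either relapse across the 3 calculated criteria", so INCAT and grip add further chances to cross. The direction is plausible, but no document gives a noise rate for either measure. The INCAT adjustment for minor arm changes and the single-rater recommendation both limit noise, so no figure can be put on it.

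Three further points stand in part:
- The interval calculation uses assumed relapse rates, and the SAP makes no decision on whether the interval excludes 0. The shrinkage of 5.6 points is small beside a 90% half-width of about 28 points at 15 per arm.
- Confirmation may lose true events. If it missed 10% or 20% of them, the 63% above would fall to 58% or 52% and the difference to 30 or 27 points, which removes most of the gain. The loss is limited because rescue and withdrawal count as relapse in any case.
- The rescue-medication analysis in SAP 8.2.9 rests on an outcome that does pass through investigator judgement, and all iRODS scores are listed.

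None of this supplies an analysis that separates sustained from single-visit crossings. The exploratory label does not help either, because the reported difference, interval and Kaplan-Meier curve are what the noise distorts.

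**Conclusion.** The point holds as a cheap improvement. A per-visit criterion is counted at any of 12 unconfirmed visits against one Baseline. The any-visit reading is not spelled out in the SAP, but it follows from relapse being counted up to Week 13 and from the time-to-relapse analysis.

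The false-relapse rate in stable participants is about 16% under independent errors and roughly 2-23% across plausible assumptions, against 2-3% for one comparison under independence. The attenuation factor (1 - f) is therefore about 0.84 under independence and between 0.77 and 0.98 over the range. It assumes the same false rate in both arms.

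The effect is confined to iRODS relapse, time to iRODS relapse and, without a defensible figure, the composite. A reader should not infer that the primary result is affected: the MMRM analyses change in the logit score and does not use the cut-off.

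**What to change.** In SAP 8.2.1 and 8.2.1.1, add a confirmed iRODS relapse beside the current definition, as the sensitivity analysis foreseen in protocol 14.3.2. Count an event when the criterion is:
- met at two consecutive scheduled iRODS assessments; or
- met at the last valid assessment before rescue or before IMP discontinuation for relapse; or
- first met at Week 13.

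Date the event to the first crossing. Report the same rate difference, 90% interval and Kaplan-Meier display, and leave the withdrawal, missing-data and rescue rules of SAP 4.2.1 as they are. State in the SAP that the current version includes single-visit crossings whose frequency depends on an unknown error correlation.

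The cost is SAP wording, one derived flag and the matching outputs, all from data already collected. The downside is that a genuine one-visit deterioration that resolves without rescue is not counted in the confirmed version, so it should supplement the current analysis and not replace it. Applying the same flag to adjusted INCAT, grip strength and the composite is optional. Sites' treatment, rescue and stopping decisions are untouched.

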### **14.3.2 Other efficacy analyses**

For the CIDP relapse (Yes/No) up to Week 13 (Day 85) after first treatment according to iRODS, adjusted INCAT, and maximum grip strength assessed by the site personnel scores, treatment comparison versus placebo for the rozanolixizumab group (differences in CIDP relapse rates) will be performed using a standard 1-sided Wald asymptotic test with a 5% alpha level. The corresponding 2-sided 90% CI for the difference will be constructed using the asymptotic standard error (asymptotic Wald confidence limits). Sensitivity analyses for relapse will be performed and described in the SAP.

For the analysis, subjects who withdraw for any reason before Week 13 (Day 85) or who have missing data at Week 13 (Day 85) will be considered as relapsed. The same is true for subjects administered an Ig infusion rescue medication during this time interval.

Kaplan-Meier estimates and log-rank tests will be used to compare the treatment difference for the time to CIDP relapse (according to iRODS, adjusted INCAT scores, and maximum grip strength assessed by site personnel).

The statistical methods applied for the variables derived from rescue medication (subject received rescue medication [Yes/No] and time to rescue medication administration) will be the same as those for the CIDP relapse and time to CIDP relapse.

For the change from Baseline at each scheduled assessment during the Treatment and Observation Period, iRODS score, adjusted INCAT score, maximum grip strength assessed by the site personnel score, and RT-MRC sum score, treatment differences will be compared by

ANCOVAs adjusted for Baseline measurement and prior Ig therapy. Analyses will be performed for the FAS utilizing the observed cases.

The results of the newly developed PROs (CIDP PRO instrument and fatigue scale) will be listed and frequency tables will be provided at an item level. A psychometric analysis plan will be created, which will detail all the exploratory and correlation analyses between the newly developed PROs and clinical variables. The PROs will also be subject to a Rasch analysis. The results of the psychometric analyses will be reported separately from the clinical study report (CSR).

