### 2.3 Study design and conduct

This is a Phase 2A, multicenter, randomized, subject-blind, investigator-blind, placebo-controlled, parallel-group study evaluating the efficacy, safety, and tolerability of rozanolixizumab for treatment of subjects with CIDP. Eligible subjects will be adults who have a confirmed diagnosis of definite or probable CIDP according to the European Federation of Neurological Societies (EFNS)/ Peripheral Nerve Society (PNS) criteria for CIDP, have been shown to be dependent on treatment with immunoglobulin and who have remained on a stable dosing regimen of immunoglobulin therapy for at least 4 months prior to Screening.

- Treatment Arm 1: rozanolixizumab [REDACTED]  
[REDACTED]
- Treatment Arm 2: placebo sc [REDACTED]  
[REDACTED]

Subjects will be randomized in a ratio of 1:1 to the 2 treatment arms. The randomization will take place on the day of first treatment with investigational medicinal product (IMP). The randomization will be stratified according to previous route of administration for Ig treatment (ie, subcutaneous immunoglobulin (SCIg) and intravenous immunoglobulin (IVIg)).

The dose level of [REDACTED] may be reduced to [REDACTED] (or equivalent placebo) for an individual subject based on their tolerability.

The study consists of:

- Screening Period of between 2 and 5 weeks duration
- The 11-week Treatment Period
- The 12-week Observation Period (from 1 week up to maximum 24 weeks):
  - All subjects completing the Treatment Period (ie, all visits up to Visit 17 performed without a CIDP relapse) will be offered the possibility to enter in the Open-Label Extension (OLE) study, CIDP04, and be treated with rozanolixizumab. If they enter in the OLE, Visit 17 will be the last study visit. The Observation Period will be limited to 1 week for these subjects.

In all other instances the subjects will perform Visits 18 to 21 for efficacy and for safety assessments. Subjects will either return to the clinic/hospital, or, if possible and agreed by both investigator and subject, have home visits conducted by certified healthcare professionals for Visits 18 and 20.

---

- For subjects who complete the Treatment Period without relapse but choose not to enter the OLE directly and wish to first test whether they still need treatment, they will continue the Observation Period without standard of care treatment.

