## **4 STATISTICAL/ANALYTICAL ISSUES**

### **4.1 Adjustments for covariates**

The regression analysis model for efficacy evaluation will adjust for the following covariates:

- Baseline score
- Route of administration of prior Ig therapy

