### 8.2.9 Use of rescue medication

The percentage of participants with concomitant medication identified as rescue medication [Yes/No] in the eCRF and time to first rescue medication administration will be summarized by treatment group and for all participants and listed by treatment group at each scheduled assessment during the Treatment and Observation Period.

If a participant receives rescue medication at multiple times, the relative day of the first occurrence is used to define the time to rescue medication.

The statistical methods applied to use of rescue medication and time to use of rescue medication will be the same as for CIDP relapse (iRODS), see Sections 8.2.1 and 8.2.1.1. The rule for handling missing data is described in Section 4.2.7.

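### Relapse and rescue differences ignore the randomisation stratum, so the coverage of their 90% intervals depends on an unknown effect of prior Ig route

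*SAP*

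**What the plan says.** Design. SAP 2.3 states "Subjects will be randomized in a ratio of 1:1 to the 2 treatment arms" and "The randomization will be stratified according to previous route of administration for Ig treatment", the two routes being subcutaneous (SCIg) and intravenous (IVIg). Protocol 5.1 and 7.9 say the same. Neither document gives a block size.

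Models. SAP 4.1 opens "The regression analysis model for efficacy evaluation will adjust for the following covariates" and lists the baseline score and route of prior Ig therapy. The mixed models for iRODS, adjusted INCAT, both grip-strength measures and RT-MRC all carry route as a fixed effect.

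Relapse and rescue. SAP 8.2.1 reports "The point estimate and the corresponding 2-sided 90% CI for the difference between placebo and rozimab CIDP relapse rates up to week 13" and adds: "The CI will be constructed using the asymptotic standard error (asymptotic Wald confidence limits". No stratum or covariate is named. Protocol 14.3.2 is also unstratified; its comparison "will be performed using a standard 1-sided Wald asymptotic test with a 5% alpha level". SAP 8.2.2 and 8.2.3 (at 14 and 8 kPa) refer back to 8.2.1, and 8.2.5 analyses any relapse in the same way. SAP 8.2.9 states: "The statistical methods applied to use of rescue medication and time to use of rescue medication will be the same". SAP 3.9, which records changes to the protocol analyses, gives no reason for leaving route out.

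Status. SAP 8 treats all efficacy analyses as exploratory and shows no p-values.

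**The concern.** Stratified randomisation makes the arms alike in route. Differences in relapse risk between routes then cancel in the treatment comparison and do not contribute to its sampling variance. A crude two-sample standard error does not know this and still counts them. Whether the reported 90% interval is close to 90% therefore depends on a route effect that nobody has specified. With p-values removed, the estimate and interval are the whole result for these variables. With about 15 evaluable participants per arm, the interval should reflect the design.

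**Working it through.** **Inputs from the documents.** Two route strata; 1:1 allocation; 15 evaluable per arm (SAP 2.4); two-sided 90% interval, so z = 1.645. SAP 2.4's own figures reproduce: a one-sided 5% t-test with 28 degrees of freedom gives 79.9% power at an effect size of 0.93 and 39.9% at 0.52, and 30/0.90 = 33.3 rounds up to 34. They concern the iRODS change. No document gives a relapse rate or a target precision for relapse or rescue.

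**Assumptions.** Relapse 60% on placebo and 30% on active; the same route gap g in both arms; IVIg:SCIg split 8:7 or 10:5 per arm; exact balance within route.

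**Step 1: variance identity.** For one arm with overall rate p and share w in one route,

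p(1−p) = average within-route variance + w(1−w)g².

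Under balance within route, the true variance of the difference uses only the first term.

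**Step 2: what the planned standard error estimates.** The crude variance at the true rates is (0.60×0.40 + 0.30×0.70)/15 = 0.0300. The between-route part is 2w(1−w)g²/15. The Wald formula plugs in observed rates, and E[p̂(1−p̂)] = p(1−p) − Var(p̂). The expected planned variance is therefore 0.0300 − V/15, where V is the true variance of the difference. For the 8:7 split, w(1−w) = (7/15)(8/15) = 0.2489:

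| Route gap | Between-route term | True variance V | Expected planned variance | Planned / true |
|---|---|---|---|---|
| 0 points | 0 | 0.0300 | 0.0280 | 0.93 |
| 20 points | 0.0013 | 0.0287 | 0.0281 | 0.98 |
| 30 points | 0.0030 | 0.0270 | 0.0282 | 1.04 |
| 40 points | 0.0053 | 0.0247 | 0.0284 | 1.15 |

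Two errors work against each other. The small-sample Wald deficit makes the interval too narrow, and the between-route term makes it too wide. Under these assumptions the sign changes between 20 and 30 points.

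**Step 3: the stratified alternative.** With n_k per arm in stratum k, Mantel-Haenszel weights are n_k·n_k/(2n_k) = n_k/2, proportional to stratum size. Under exact balance the point estimate equals the crude difference. Its variance estimate is Σ(n_k/n)²[p̂₀ₖ(1−p̂₀ₖ) + p̂₁ₖ(1−p̂₁ₖ)]/(n_k−1).

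**Step 4: coverage and width** (at least 100,000 simulated trials per scenario, 8:7 and 10:5 splits):

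| Route gap | Planned Wald coverage | Stratified n−1 coverage | Stratified width / planned width |
|---|---|---|---|
| 0 points | 87.5–87.8% | about 90% | 1.03 |
| 20 points | about 88.6% | about 90% | 1.01 |
| 30 points | about 89.6% | 89–90% | 0.98 |
| 40 points | 90.7–91.2% | about 89% | 0.93–0.94 |

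With no gap the mean widths are 0.549 (planned) and 0.568 (stratified). At 30 points and 8:7 they are 0.551 and 0.538. A plain stratified Wald interval, without n−1, covers only about 86%.

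**Step 5: separating the two changes.** Give the crude interval the same n−1 correction, and its width is 0.568 with no gap, equal to the stratified one. At 20, 30 and 40 points the stratified interval is then about 2.5%, 5–6% and 9–10% narrower. The extra width at small gaps in Step 4 therefore comes from the n−1 correction, not from stratifying.

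**Step 6: sensitivity.** If one route is rare the gain shrinks. At a 30-point gap the stratified-to-planned width ratio is 0.997 for a 12:3 split and 1.008 for 13:2. Coverage also varies with the rates. At 10:5, with placebo relapse 70%/30% by route and active 35%/15%, the stratified n−1 interval covers 87.9% and the planned one 89.5%. With 70%/30% in both arms the figures are 89.1% and about 92.5%.

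**The case against.** The strongest reply has four parts.

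- **No gain without a large route effect.** Against the interval actually planned, the stratified one is wider at gaps of 0 and 20 points and narrower only from about 30. The documents give no route effect, no route split and no block size. Both regimens had to be stable with confirmed Ig dependency, so a gap of 30 to 40 points is speculative. This stands, and it limits the size of the point.
- **No bias.** With balance within route, the stratified and crude estimates coincide; only the interval changes. This stands.
- **No inconsistency.** SAP 4.1 confines route adjustment to the regression model, and 8.2.1 follows Protocol 14.3.2. This also stands. A reader might infer that the SAP breaks its own covariate rule, but the text does not say so. The point is a design feature left unused, not a contradiction.
- **Exploratory status.** Relapse and rescue are listed among the other efficacy variables, so no formal decision rests on them. This lowers the stakes, but the interval is still the reported result.

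The reply does not remove the mechanism. The planned interval's coverage moves with a quantity outside the plan's control, and a design-based interval is much less sensitive to it in the main scenarios.

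**Conclusion.** The concern holds in a limited form. The relapse and rescue differences leave out the randomisation stratum, so the calibration of their 90% intervals depends on the unknown route effect. In the main scenarios, planned coverage runs from about 87.5% to 91.2% across gaps of 0 to 40 points, against about 89–90% for the stratified n−1 interval. Widths change by +3% to −7%.

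A reader might infer that the planned interval is simply too wide and that stratifying always gains precision. The documents do not support that. They specify the uncorrected Wald interval, which is slightly too narrow at small route gaps, and they contain no evidence of a large gap. The larger gains in Step 5 apply only against a corrected crude interval that the SAP does not plan.

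All figures rest on the assumed rates, route split and exact balance. The consequence is modest, concerning coverage and precision only, and the analyses are exploratory. The change is worth making because it is cheap and follows the design.

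**What to change.** In SAP 8.2.1, carried by reference into 8.2.2, 8.2.3, 8.2.5 and the rescue-use proportion in 8.2.9:

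- Report the Mantel-Haenszel-weighted risk difference stratified by prior Ig route as randomised.
- Give a small-sample stratified 90% interval, either with n−1 within-stratum variances or a stratified score interval. Do not use a plain stratified Wald interval.
- Keep the crude difference as a supportive line.
- State the source of the stratum. SAP 3.9 defines prior Ig therapy by the stratification factor, while 8.1.2 takes route from the eCRF medication form.

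The cost is a few sentences and a few lines of programming, with no new data. The interval would be about 3% wider than planned if route has no effect, and the gain is small or absent if one route is rare.
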